11.5 Packaging and Labeling

Study drug will be supplied by Vertex. VX-509 will be provided as 50-mg tablets. VX-509-matched placebo tablets will be the same size but will not contain any active drug. These tablets will be packaged into weekly blister cards. Study drug labeling will be in compliance with applicable local and national regulations.

Additional details regarding packaging, labeling, and dispensing for VX-509 and placebo will be included in the Pharmacy Manual.

11.6 Study Drug Supply, Storage, and Handling

The investigator, or an authorized designee (e.g., a licensed pharmacist), will ensure that all investigational product is stored in a secured area, under recommended storage conditions and in accordance with applicable regulatory requirements.

Detailed instructions regarding the storage and handling of VX-509 and placebo will be provided in the Pharmacy Manual.

11.7 Compliance

On Day 1, the dose will be administered under the direct supervision of the investigator or designee.

For study drug doses administered during the outpatient periods of the study, drug accountability will be assessed at each visit by counting returned dosage units. Subjects will be instructed to bring all used and unused study medication supplies, including empty blister packs, to each visit. Discrepancies will be discussed with the subject and recorded in the source documents.

If subjects demonstrate continued non-compliance of study drug dosing despite educational efforts, the investigator should contact the medical monitor to discuss discontinuation of the subject from the study.

11.8 Drug Accountability

Study drug may be dispensed only under the supervision of the investigator or authorized designee and only to study subjects. The pharmacist or designated site staff will maintain information regarding the dates and amounts of (1) study drug received; (2) study drug dispensed to subjects; and (3) study drug returned by the subjects. Subjects will be instructed to return all used and unused materials associated with the study drug to the study site. These materials will be retained at the study site according to instructions provided by Vertex, or its designee, until inventoried by the study monitor. The study monitor will review study drug records and inventory throughout the study.

11.9 Disposal, Return, or Retention of Unused Drug

The site staff or pharmacy personnel will retain all materials returned by the subjects until the study monitor has performed drug accountability. At the end of the study, Vertex will provide instructions as to the disposition or return of any unused investigational product. If the site has a drug destruction policy in place and drug destruction capabilities, Vertex may authorize destruction at the study site. In such cases, the investigator must ensure that the materials are destroyed in compliance with applicable environmental regulations,

institutional policies, and any special instructions provided by Vertex. Adequate documentation of study drug destruction must be provided.

11.10 Blinding and Unblinding

This will be a double-blind, placebo-controlled study. As an exception, the subjects in the Synovial Biopsy Subset will only be randomized to the 200 mg qd dose of VX-509 (Arm C). Subjects in the Synovial Biopsy Subset will know that they are not receiving placebo, but not the dose they are receiving.

11.10.1 Blinding

Blinding of all data will be maintained until the study database is locked. The packaging and labeling of study drug will be performed in a way that ensures dose levels are blinded. Investigators and site personnel will be blinded to drug concentrations during VX-509 dosing.

All study personnel will be blinded to subject treatment assignments except for the following individuals: an unblinded Vertex statistician who is not a member of the study execution team, Vertex Global Patient Safety and Regulatory Affairs representatives when required to satisfy regulatory reporting requirements, and Vertex bioanalytical scientist(s) or designee (as specimens from subjects randomized to placebo will not be routinely analyzed for PK).

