9.2 Rationale for Study Design and Study Drug Regimens

9.2.1 Study Design

The study is designed to evaluate early response to VX-509 administration, including local synovial and bone response assessment by MRI imaging and synovial biopsy (Section 6.5). The double-blind placebo-controlled design will allow comparison to variability in efficacy parameters for control subjects. No blinded joint assessor is utilized in the trial due to the small subject numbers and partial unblinding of all arthroscopy subjects, who are randomized to the 200 mg qd dose of VX-509 (Arm C) to avoid the variability inherent with doseranging. Due to the increased assay sensitivity of joint MRI, and blinded reading by 2 central readers, there is improved study power to detect RAMRIS differences and the validity of MRI data is maintained. As a sensitivity analysis, the ACR20-CRP and DAS28-4(CRP) efficacy parameters will be re-evaluated without inclusion of the arthroscopy subjects.

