9.2.5 Previous Clinical Findings

In 3 Phase 1 studies, VX-509 was administered as single doses from 10 to 900 mg, and as multiple daily doses of 25 to 600 mg for 7 or 14 days (Study VX08-509-001, Study VX08-509-002, and Study VX10-509-004). Overall, the results demonstrated that VX-509 was safe and well-tolerated with administration of multiple doses of up to 600 mg daily for 14 days in normal healthy volunteers. One subject receiving a single 900 mg dose of VX-509 developed symptoms of nausea, vomiting, headache, and tremor. This subject was found to have a higher plasma VX-509 exposure (173 μg•hr/mL), which exceeded the exposure level at the NOAEL in all nonclinical species.

Data from a 12-week Phase 2a study (Study 101) of VX-509 administration in 204 RA subjects demonstrated that ACR20-CRP responses at Week 12 were achieved in 29%, 39%, 61%, 65% and 66% of the placebo, 25-, 50-, 100- and 150-mg bid VX-509 groups, respectively ($P \le 0.007$ for the 3 highest doses). Statistically significant improvement was also seen for the 3 highest doses in DAS28-4(CRP) at Week 12 (P < 0.001).

The most frequent adverse events (AEs) were infections, seen in approximately 17% of both placebo and VX-509 subjects, although more frequently in higher VX-509 dose groups. There were 11 treatment-emergent serious adverse events (SAEs) seen in 9 subjects (10 SAEs in 8 VX-509 subjects) and SAEs were more frequent in the higher VX-509 dose groups. There were 5 SAEs in the infections and infestations system organ class, all in subjects receiving VX-509, including bronchitis, erysipelas, pneumonia, tuberculosis, and osteomyelitis. There were 2 fatal SAEs of subarachnoid hemorrhage and pneumonia in VX-509 subjects.

Primarily Grade 1 increases ALT or AST values, and increases in both low density lipoprotein (LDL)- and high density lipoprotein (HDL)-cholesterol were observed in subjects who received higher doses of VX-509. For further information refer to the VX-509 Investigator's Brochure.³⁵

^a In Study VX09-509-101, estimated AUC_{0-24h} for 300 mg qd was 33.4 μg•hr/mL (Table 9-2).

Uterine and mammary gland atrophy are considered to be rat species-specific findings.³⁶ Based on the male rat NOAEL (60 mg/kg/day), the safety margin for female rats would also be 2.68.

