12.9.2 Clinical Laboratory Assessments

Blood and urine samples for the procedures described in Table 12-1 will be analyzed at a local or central laboratory. Subjects must abstain from all food and drink (except water) at least 8 hours before blood draws for the fasting lipid profile. Laboratory test results that are abnormal and considered by the investigator to be clinically significant must be reported as adverse events.

Table 12-1 Safety Laboratory Test Panels

Serum Chemistry	Hematology	Urinalysis
Glucose	Hemoglobin	Leukocytes
Blood urea nitrogen	Red blood cell count	Nitrite
Creatinine	Mean corpuscular hemoglobin	Urobilinogen
Creatine kinase	Mean corpuscular hemoglobin concentration	Protein
Sodium	Mean corpuscular volume	рН
Potassium	Platelet count	Blood
Calcium	Reticulocyte count	Specific gravity
Chloride	White blood cell count	Ketones
Magnesium	Differential (absolute and percent):	Bilirubin
Inorganic phosphate	Eosinophils	Glucose
Total and indirect bilirubin	Basophils	
Alkaline phosphatase	Neutrophils	Microscopy: *
Aspartate transaminase	Lymphocytes	Casts
Alanine transaminase	Monocytes	Bacteria
Lactate dehydrogenase		Red blood cells
Total protein		White blood cells
Albumin		
Uric acid		* If gross urinalysis is positive
Iron Studies (baseline only)		for leukocytes, erythrocytes,
Serum iron		nitrite, protein, or bilirubin, microscopic examination of
Ferritin		urine will be performed.
Total iron-binding capacity		will be performed.

Additional Evaluations

Coagulation studies: Activated partial thromboplastin time; prothrombin time; and International Normalized Ratio.

Inflammation tests: C-reactive protein, and Westergren erythrocyte sedimentation rate

Fasting lipid profile: Total Cholesterol, HDL-C, LDL-C, LDL-C/HDL-C ratio, triglycerides. Leptin and lipoprotein (a) will be assessed as part of this profile only on Day 1 and at the Week 12/Early Discontinuation Visit.

Erythropoietin

Serology: Hepatitis B surface antigen, hepatitis C virus antibody, human immunodeficiency virus 1 antibody, and human immunodeficiency virus 2 antibody.

Tuberculin skin testing: A 5 tu purified protein derivative (PPD) skin test will be positive if >10 mm at 48 to 72 hours.

QuantiFeron® **TB Gold Assay**: Serum incubation and enzyme-linked immunosorbent assay (ELISA) testing for latent tuberculosis.

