14.1.1.2 Clinically Significant Assessments

Study assessments including laboratory tests, ECGs, physical examinations, and vital signs should be assessed and those deemed a clinically significant worsening from baseline documented as an adverse event. When possible, a clinical diagnosis for the study assessment should be provided, rather than the abnormal test result alone (e.g., urinary tract infection, anemia). In the absence of a diagnosis, the abnormal study assessment itself should be listed as the adverse event (e.g., bacteria in urine or decreased hemoglobin).

An abnormal study assessment is considered clinically significant if the subject has or requires 1 or more of the following:

- Concomitant signs or symptoms related to the abnormal study assessment
- Further diagnostic testing or medical/surgical intervention
- A change in the dose of study drug or discontinuation from the study

Repeat testing to determine whether the result is abnormal, in the absence of any of the above criteria, does not necessarily meet clinically significant criteria. The determination of whether the study assessment results are clinically significant must be made by the investigator.

A laboratory abnormality judged to be Grade 4, in itself, may not constitute an SAE unless the clinical status of the subject indicates a life-threatening adverse event.

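### No rule masks on-treatment CRP from sites, and no independent joint assessor is used, so joint and physician-global scoring for ACR20-CRP and DAS28-4(CRP) can be influenced by known laboratory response

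*Protocol*

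**What the plan says.** - **Blinding (Protocol 11.10.1).** The section opens with a general statement: "Blinding of all data will be maintained until the study database is locked". The one result it names as withheld from sites is the drug concentration: "Investigators and site personnel will be blinded to drug concentrations during VX-509 dosing". Study personnel are blinded to assignment, apart from listed sponsor roles.
- **Laboratory tests (12.9.2, Table 12-1).** "Blood and urine samples for the procedures described in Table 12-1 will be analyzed at a local or central laboratory". The table's inflammation tests are "C-reactive protein, and Westergren erythrocyte sedimentation rate", and it also contains the fasting lipid profile.
- **Who judges the results.** Section 12.9.2: "Laboratory test results that are abnormal and considered by the investigator to be clinically significant must be reported as adverse events". Section 14.1.1.2: "The determination of whether the study assessment results are clinically significant must be made by the investigator".
- **Timing (Table 3-2).** After Day 1, CRP and WESR are drawn at Weeks 2, 6, 8 and 12 (also Week 4 in the biopsy subset) and at follow-up. Lipids are drawn at Weeks 2, 6 and 12 and at follow-up.
- **Joint scoring (9.2.1).** "No blinded joint assessor is utilized in the trial due to the small subject numbers and partial unblinding of all arthroscopy subjects".
- **Known laboratory effects (9.2.5).** In the earlier Phase 2a study, mainly Grade 1 ALT or AST rises and increases in LDL and HDL cholesterol "were observed in subjects who received higher doses of VX-509".

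**The concern.** ACR20-CRP and DAS28-4(CRP) are primary endpoints with a large assessor-scored part. A falling CRP tells the assessor that the subject is responding, and it is also part of the endpoint. If that knowledge colours the joint counts or the physician global, components meant to be scored separately come to agree. A lipid rise could in addition hint at a higher dose.

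Bias of this kind would tend to favour VX-509. If it followed dose, it would resemble the pattern that the trend tests in 13.3.3.1.1 and 13.3.3.1.2 look for. Section 13.3.4.7 allows interim analyses that include both endpoints to inform Phase 3 dose selection, so more than description is at stake.

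**Working it through.** **1. Is on-treatment CRP masked anywhere?** The general sentence in 11.10.1 cannot mean that laboratory values are hidden from sites. Investigators must judge their clinical significance (12.9.2, 14.1.1.2) and must act on transaminases during treatment (12.9.3). No other section sets a masking rule for CRP or WESR. Access for the joint assessor is therefore permitted, though nowhere stated as fact.

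**2. How much of each endpoint does the assessor score?**
- ACR20 (16.10) requires 20% improvement in both joint counts and in 3 of 5 other items. The assessor scores both required counts and one of the five, the physician global. A subject with three of the remaining four items improved (pain, subject global, disability, CRP) is decided by the joint counts alone. A subject with two of the four improved is decided by the joint counts and the physician global together. A subject with fewer than two cannot be made a responder by the assessor.
- DAS28-4(CRP) (16.8) has joint terms 0.56√TJC28 + 0.28√SJC28. Illustration: scoring 8 tender and 6 swollen joints instead of 10 and 8 changes the score by 0.56(3.162 − 2.828) + 0.28(2.828 − 2.449) = 0.187 + 0.106 = 0.29.

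**3. Do the existing safeguards reach this route?**
- Central MRI reading by two readers blinded to dose and chronology (12.8.1) protects RAMRIS only.
- The sensitivity analysis (13.3.3.4) removes biopsy subjects, who number about 6 and at most 10 (9.1). At least 40 − 10 = 30 subjects remain, scored in the same way.

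**4. The protocol's own figure.** Section 13.1 gives about 25% power for 25% versus 65% with 10 per arm. An exact two-sided Fisher test at 0.05 (test and level assumed) gives 24.5%. The figure is reproduced and is not in dispute.

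**5. What a given bias would do.** The protocol gives no size, so shifts of 10 and 20 points are assumed, with a true ACR20 rate of 25% in every arm.

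*Miettinen-Nurminen 95% interval, one dose against placebo.* The interval lies wholly above 0 when z = (p₁ − p₀) / √[p̄(1 − p̄)(1/10 + 1/10)(20/19)] exceeds 1.96. Summing the binomial probabilities of all such outcomes gives:

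| Apparent rates | Chance of wrongly favouring the dose |
|---|---|
| 25% v 25% | 1.7% |
| 25% v 35% | 5.4% |
| 25% v 45% | 12.7% |

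One subject can decide the result. For 2/10 v 6/10, z = 0.4/0.225 = 1.78. For 2/10 v 7/10, z = 0.5/0.228 = 2.19.

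*Cochran-Armitage trend, upper tail at 1.96.* With scores s = 0, 1, 2, 3, z = Σs(x − 10p̄) / √[10 p̄(1 − p̄) × 5], where 5 = Σ(s − 1.5)². Exact enumeration gives:

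| Apparent rates, placebo to 300 mg | False positive trend |
|---|---|
| 25/25/25/25 | 2.6% |
| 25/28/32/35 | 7.7% |
| 25/30/35/40 | 11.8% |

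These tables show sensitivity to an assumed bias. They do not show that CRP or lipid reports would produce it.

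**The case against.** - **A reader might infer that sites see every post-dose result.** The protocol does not say so. Blood Biomarker Sample A is stored by the sponsor, and release of Sample B or flow cytometry results to sites is not described (12.6.1). What is supported is the absence of a masking rule for CRP and WESR.
- **A reader might infer that CRP or lipids identify the arm.** Section 9.2.5 ties dose to lipids and ALT/AST, not to CRP, and gives no size or overlap between arms. CRP signals response, not assignment, and could also fall in a subject on placebo.
- **A reader might take 9.2.1 to mean that assessors know the treatment.** Section 11.10.1 keeps study personnel blinded to assignment. What is missing is an assessor kept apart from the subject's other data. That is a disclosed choice with two stated reasons. The biopsy reason does not cover the other subjects, but small numbers do apply to the whole trial.
- **The assessor's control of ACR20 is limited.** This stands, as step 2 of the working shows.
- **The consequences are muted.** Section 13.1 says the trial is not powered for comparisons with placebo and points to RAMRIS for choosing the Phase 3 dose. This lowers the stakes. It does not remove them, because the two clinical endpoints are also primary and may enter the interim dose-selection analyses.
- **Masking lipids as well would do harm.** This stands. It would conflict with investigator review (12.9.2, 14.1.1.2) and could deplete the dyslipidemia adverse-event summary (13.3.4.6). ALT/AST would still be visible.

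**Conclusion.** The point holds in a limited form. The protocol leaves on-treatment CRP unmasked and uses no independent joint assessor, so ACR20-CRP and DAS28-4(CRP) are open to bias from knowledge of laboratory response. Neither planned safeguard covers this, and the RAMRIS endpoints are not affected.

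The size is unknown. The error rates above rest on an assumed 10- to 20-point shift, a true 25% rate in every arm and 10 subjects per arm. The documents do not show that unblinding would occur or that an individual report would reveal the arm. The case for change is that the remedy is cheap and each subject is worth 10 percentage points in an arm.

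**What to change.** In Sections 11.10.1 and 12.9.2:
1. State that post-baseline CRP is analysed centrally and withheld from sites and from the blinded study team until database lock. Results should stay out of the data-capture system until then, because 14.3 gives the sponsor access to data on entry. Screening and baseline CRP are unaffected.
2. Require joint counts and the physician global to be recorded before any laboratory report for that visit, including WESR, is opened.
3. Leave lipids and the other safety results available for investigator review, and acknowledge that lipids and ALT/AST remain a residual route to unblinding.

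**Cost.** CRP can no longer be run locally, and the investigator-review wording in 12.9.2 needs an exception for it. Sites lose on-treatment CRP as routine clinical information, although neither 9.1.4 nor 12.9.3 lists it among the values that prompt interruption or discontinuation. No staff or procedures are added. The order rule does not hide results from earlier visits, so past WESR, lipid and liver values stay visible to the assessor.

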11.10.2 Unblinding

The following are the limited circumstances where unblinding may be performed.

11.10.2.1 Unblinding: PK/PD Analyses

The Vertex clinical pharmacologist or designated clinical pharmacology vendor may request unblinded VX-509 and biomarkers data with masked subject identification numbers and true treatment assignments (Section 13.4).

A limited internal Vertex clinical pharmacology team will be unblended to subject randomization data for purposes of performing the PK analysis. However, other Vertex staff, clinical site staff, and subjects will remain blinded through study Data Lock.

11.10.2.2 Unblinding: Interim Analyses

An unblinded Biostatistician may perform an IA as described in Section 13.3.4.7. The unblinded Biostatistician may request unblinded interim data with true subject identification (ID) numbers and true treatment assignments, as will be specified in an Interim Analysis Statistical Analysis Plan.

11.10.2.3 Unblinding: Final Analysis

The Vertex study biostatistician or designee may request blinded final data after Week 12 with true subject ID numbers and dummy treatment assignments. Details will be provided in the Statistical Analysis Plan (SAP). The Vertex study biostatistician or designee may request unblinded final data after data lock with true subject ID numbers and true treatment assignments. Details will be provided in the SAP.

11.10.2.4 Unblinding: Drug Supply Quality Control at Study Sites and Depots

The Vertex Quality Assurance group or its designee will perform quality control/assurance inspections at study sites and drug supply depots. For those Vertex representatives who need access to unblinded data to perform this audit, they may request to be unblinded to true subject identification numbers and true treatment assignments.

11.10.3 Unblinding: Medical Emergencies or Urgent Clinical Situations

At the initiation of the study, each clinical study site will be instructed on the method for breaking the blind. The unblinding method will be either a manual or an electronic process.

Unblinding of individual subject treatment by the investigator should be limited to medical emergencies or urgent clinical situations in which knowledge of the subject's study treatment is necessary for clinical management. In such cases, the investigator must first attempt to contact the study medical monitor (see relevant telephone numbers provided in a separate contact information document), to discuss and agree to the need for unblinding. In situations in which the investigator has attempted and failed to contact the medical monitor, investigators should use their best judgment, based on the nature and urgency of the clinical situation, and proceed with unblinding.

Detailed instructions for unblinding in the case of medical emergencies will be provided in the study manual.

Once a subject's treatment assignment has been unblinded for a medical emergency or urgent clinical situation, the medical monitor and study team should be notified within 24 hours of unblinding of the treatment. Information relating to unblinding (reason, date, etc.) should be clearly recorded in the subject's study file. In addition, the investigator should consider whether the clinical event that prompted unblinding should be considered a serious adverse event (SAE), according to the regulatory definitions or criteria for SAEs, and if so, submit an SAE report to Vertex Global Patient Safety or its designee.

Vertex Global Patient Safety or its designee will also unblind any SAE reports in compliance with regulatory reporting requirements. In addition, Vertex Global Patient Safety may, for matters relating to safety concerns, unblind individual subjects at any time.

12 ASSESSMENTS

12.1 Timing of Assessments

The timing of assessments is shown in Table 3-1 and Table 3-2.

12.2 Subject and Disease Characteristics

Subject and disease characteristics will include the following: demographics, medical history (including allergies and vaccination history), RA medical history [(including RA duration and past RA therapies based on subject recall (no external documentation required)], height, weight, body mass index (BMI), and social characteristics (smoking and alcohol history).

